Coronary heart disease is the leading cause of death in the United States and a major cause of disability. Cardiac rehabilitation programs that include an exercise training intervention have been shown to reduce cardiac mortality by approximately 25%, with improved exercise tolerance and peak oxygen consumption, and a concomitant improvement in functional status and quality of life. Unfortunately, many patients entering cardiac rehabilitation programs do not complete them, and the increase in exercise capacity among completers is variable. Although psychosocial factors are important predictors of successful cardiac rehabilitation, one common but often undiagnosed barrier to successful rehabilitation is the presence of obstructive sleep apnea (OSA), which is highly prevalent in patients with coronary heart disease. Obstructive sleep apnea is a common condition in adults, associated with recurrent airway collapse during sleep resulting in intermittent hypoxemia and sleep fragmentation. Two studies of OSA in patients undergoing cardiac rehabilitation suggest prevalence in excess of 50%. While OSA is strongly associated with obesity, studies of exercise training in patients with OSA demonstrate a poorer response to exercise independent of body habitus. The sleepiness and fatigue caused by OSA may contribute to impaired motivation to exercise, although intermittent hypoxia itself has been shown to decrease ventilatory efficiency in healthy adults. Patients with OSA have reduced exercise tolerance compared to obese controls, and treatment of OSA with continuous positive airway pressure (CPAP) results in increased peak oxygen consumption on symptom-limited exercise testing and an increase in constant load exercise time. These studies suggest that treatment of OSA might substantially improve the response to exercise training as part of cardiac rehabilitation, although

these were uncontrolled case series in general patients with OSA, not in the setting of cardiac rehabilitation.

(b) Hypothesis

We hypothesize that identification and treatment of obstructive sleep apnea (OSA) in patients with comorbid OSA and coronary heart disease undergoing cardiac rehabilitation will improve their response to rehabilitation.

(c) Specific Objectives

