- Physician diagnosis of ischemic heart disease, with prior myocardial infarction or coronary revascularization procedure
- Referral to the Cardiac Rehabilitation Program
- Epworth Sleepiness Scale $<$ 18
- Ability to provide informed consent

For continuing to randomization, the following additional inclusion criterion applies:

- Moderate to severe obstructive sleep apnea, defined as an apnea-hypopnea index \geq 15 events per hour, with $>$ 50% of events being obstructive apneas or hypopneas

Exclusion criteria:

- Poorly controlled hypertension (>170/>110), poorly controlled diabetes (HbA1c > 9.0), severe renal failure with estimated glomerular filtration rate <30 ml/min, prior stroke with functional impairment or other severe, uncontrolled medical problems that may impair ability to participate in the study exams, based on medical history and review of medical records
- Severe daytime sleepiness, defined as Epworth Sleepiness Scale score 18 or higher or a report of falling asleep driving during the previous year
- Awake resting oxyhemoglobin saturation <89%
- Pregnancy
- Current use of a positive airway pressure device (including continuous or bi-level positive airway)

Study Design

The proposed study is a randomized, parallel group study comparing 8 weeks of therapy with continuous positive airway pressure (CPAP) to an educational control for patients with comorbid obstructive sleep apnea and coronary heart disease undergoing a structured cardiac rehabilitation program. The primary study outcome measure, to be made at baseline and at end of the treatment period, is change in walking distance and speed as measured by 6 minute walk test, a valid and reproducible measure of functional capacity. The primary analysis will compare the active treatment group to the control group. Secondary outcome measures include measures of functional status and health related quality of life, and adherence to cardiac rehabilitation.

Sample Selection

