is no respiratory effort during the event. Identification of hypopneas will require: (1) a fall in peak signal excursion of $\geq 30\%$ from the pre-event baseline, using nasal pressure as the preferred sensor; (2) an event duration of at least 10 seconds; and (3) an associated $\geq 3\%$ fall in oxyhemoglobin saturation from the pre-event baseline. Studies that do not meet minimal quality grades (4 hours of scorable record) will be repeated.

Patients who have had a recent sleep study demonstrating the presence of sleep apnea meeting criteria for inclusion in this study, but not yet treated, may proceed to randomization without repeating the portable sleep study.

Baseline (randomization) visit

Participants with at least moderate obstructive sleep apnea (AHI >15 , with $>50\%$ obstructive events) on home sleep testing will proceed to the baseline study visit. The entire baseline visit is expected to take approximately 15 minutes.

Anthropometry

- Height and weight
- Waist, hip, and neck circumference

Cardiac Rehab Assessment Measures

Information from the participant's initial assessment for Cardiac Rehabilitation will be pulled from the Cardiac Rehabilitation exercise evaluation note in CPRS. Measures of particular interest include strength, balance, and range of motion assessments as well as results from the 6 min walk test. Participants' responses to World Health Organization Disability Assessment Scale II (WHODAS II) (21) will also be recorded.

Randomization

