Baseline data will be summarized using standard descriptive statistics for demographic and baseline clinical characteristics by treatment group. Based on our experience with the HeartBEAT Study, the rate of dropouts during the course of the three-month trial is expected to be low and we do not expect dropouts to be differential with respect to treatment group assignment. The main analysis will include all subjects completing the follow-up examination. For the purposes of a sensitivity analysis, a result of “no change” will be imputed for all dropouts, and compared to the main analysis.

The analysis for the primary outcome measure will consist of a one-factor analysis of variance comparing the mean changes from baseline in six minute walk distance. The primary analysis is a simple analysis of variance, with data transformation or adoption of rank-based inference if approximate normality is not present. A p value <0.05 will be considered statistically significant. While the randomization should achieve approximate balance on potentially confounding conditions, analysis of covariance models that employ adjustments for age, sex, sleep apnea severity, comorbid illness, smoking and alcohol use will be fit to potentially improve the efficiency of the treatment effect estimates. Should a significant difference between treatment and comparator be identified, further exploratory analyses will assess the relation of adherence to CPAP therapy to change in outcome measures.

Each of the secondary outcome measures is continuous; therefore, analysis of these variables will be treated in a similar fashion to the analysis of the primary study endpoints.

Sample size and power

Our primary goal is to determine the impact of identification and treatment of obstructive sleep apnea in patients with coronary heart disease undergoing cardiac rehabilitation. Patients will be allocated into the two groups, HLSE or HLSE plus CPAP, randomly according to a 1:1 ratio.

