There are no published data on the effect of CPAP therapy on 6-minute walk distance in patients with coronary heart disease; however, in a recent report from a general sample of patients with OSA, treatment with CPAP was associated with a mean 114 m improvement in 6-minute walk distance after 4 weeks, compared to a control group not treated with CPAP (22). This is well above the minimal clinically important difference of 23 m in 6-minute walk distance reported for patients with stable coronary heart disease (23). The standard deviation in 6-minute walk distance in patients with stable coronary

heart disease has been estimated at 104 m (24), similar to the 90 m estimated for healthy adults (25). Assuming a modest correlation of 0.4 between repeated measures of the 6-minute walk test, the sample size of 25 subjects in each group will have 80% power to detect a difference between groups of 57 m in 6-minute walk distance, half of the difference reported for the effect of OSA treatment (22).

Human Subjects

Potential Risks

The study procedures do not place the subjects at risk of harm or discomfort greater than those encountered in routine medical care. Portable sleep monitoring may lead to minor sleep disturbance and some subjects may experience mild skin irritation from the sensors or electrodes used. The administration of questionnaires may be stressful, although none ask sensitive information.

The study treatment is generally considered quite safe. CPAP is a FDA-approved therapy for the treatment of sleep apnea. The use can be associated with a number of minor side effects, including nasal congestion, runny nose, dry nose or mouth, skin irritation from the mask or headgear, aerophagia or discomfort from the mask or air pressure. Rarely, sinus problems may get worse while using CPAP and mild nose bleeds may occur. These side effects will be minimized by using a humidifier built into the device and by using the most appropriate pressure.

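### The primary ANOVA on change is unadjusted and the supporting ANCOVA omits baseline walk distance; adding it would cut the variance of the treatment effect by 28–30% at the plan's correlation of 0.4, and by less at higher correlations

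*Combined protocol and SAP*

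**What the plan says.** The Study Design section names change in 6-minute walk performance as the primary outcome, with measurements "to be made at baseline and at end of the treatment period". The Statistical analysis section specifies a "one-factor analysis of variance comparing the mean changes from baseline in six minute walk distance" and repeats that this is a simple analysis of variance, moving to a transformation or rank-based inference if normality fails. With two groups it is a t test on change.

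The same section adds covariance models in which "adjustments for age, sex, sleep apnea severity, comorbid illness, smoking and alcohol use will be fit", with the aim "to potentially improve the efficiency of the treatment effect estimates". Baseline walk distance is not on that list or named as a covariate anywhere else. It is available: under Cardiac Rehab Assessment Measures, the intake note supplies "range of motion assessments as well as results from the 6 min walk test".

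The Sample size and power section gives an SD of 104 m in stable coronary heart disease, 25 per group and 80% power at 57 m, "Assuming a modest correlation of 0.4 between repeated measures of the 6-minute walk test".

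**The concern.** A change score subtracts the whole baseline value, which amounts to fixing the slope of follow-up on baseline at 1. With equal SDs at the two visits that slope equals the correlation, which the plan puts at 0.4. The planned test therefore over-corrects for baseline and carries avoidable noise. The ANCOVA is justified by efficiency, yet it leaves out the one variable for which the plan itself states a correlation with the outcome.

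In a trial of 50 patients this widens the interval for the primary effect more than the data require. It also means that a chance baseline difference between the arms passes into the estimate. Bias over repeated randomizations and false-positive risk are not at issue.

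**Working it through.** **Inputs.** From Sample size and power: SD 104 m, correlation ρ = 0.4, n = 25 per arm, target difference 57 m. From Statistical analysis: p < 0.05, taken as two-sided because sidedness is not stated. Assumed: normal data, a common slope, and equal SDs at both visits (the plan gives a single SD).

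**The plan's own figure.** SD of change = 104 × √(2 × (1 − 0.4)) = 113.9 m. The standard error of the contrast is 113.9 × √(2/25) = 32.2 m. Power at 57 m is 41% by noncentral t (42% by normal approximation), not the stated 80%. Keeping 57 m, 80% and SD 104 m with a change score requires ρ of about 0.76 (normal) or 0.77 (t). The value 0.76 used below is back-solved in this way and is not in the documents.

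**Variance comparison.** In units of the single-visit variance:
- Change score: 2(1 − ρ) = 1.20.
- ANCOVA on baseline: 1 − ρ² = 0.84.
- Large-sample ratio: 0.84/1.20 = 0.70, a 30% reduction.
- Cost of estimating the slope: 1 + 1/(2n − 4) = 1 + 1/46 = 1.0217, so the ratio is 0.70 × 1.0217 = 0.715, a 28.5% reduction.
- Simulation of 60,000 trials: 28.8%.

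**What this means at 25 per arm, ρ = 0.4.** ANCOVA ranges run from the slope estimated to the slope taken as known.

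| | Change-score ANOVA | ANCOVA on baseline |
|---|---|---|
| Power at 57 m | 41% | 53–54% |
| Difference detectable with 80% power | 92 m | 77–78 m |
| 95% interval half-width | 65 m | 54–55 m |
| Per arm for 80% power at 57 m | 64 | 46 |

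The change score would need 25/0.715 ≈ 35 per arm to match ANCOVA at 25. In null simulations (100,000 trials) type I error was 0.050 for both tests.

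**Dependence on the inputs.** With k = follow-up SD / baseline SD, the variance ratio is k²(1 − ρ²)/(1 + k² − 2ρk) × 1.0217.

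| ρ | Reduction, k = 1 | Reduction, k = 1.2 (assumption) |
|---|---|---|
| 0.4 | 28.5% | 16.5% |
| 0.6 | 18% | 6% |
| 0.7 | 13% | 1% |
| 0.76 | 10% (12% large-sample) | 1% loss |
| 0.9 | 3% | not computed |

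With k = 1 the break-even is ρ = 0.957. The first factor never exceeds 1, so ANCOVA can never cost more than about 2% in variance.

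**Against the six-factor ANCOVA.** In simulation (8,000 trials, outcome change, ρ = 0.4), adding baseline distance cuts variance by 29% if the six factors predict nothing. It cuts it by 41% if they explain 30% of walk-distance variance at each visit with equal effects. The second case is an assumed scenario; it implies a correlation after adjustment of (0.4 − 0.3)/0.7 = 0.14.

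**Baseline imbalance.** The between-arm baseline difference has standard error 104 × √(2/25) = 29.4 m, so the chance that it exceeds 23 m in either direction is 43%. The plan cites a "minimal clinically important difference of 23 m in 6-minute walk distance". An imbalance of 23 m shifts the expected change contrast by (1 − 0.4) × 23 = 14 m, or (1 − 0.76) × 23 = 5.5 m at ρ = 0.76. ANCOVA removes this shift on average. It is the same loss seen conditionally, not an additional one: (1 − 0.4)² = 0.36 = 1.20 − 0.84.

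**The case against.** The strongest reply is that nothing here is an error. The plan names one outcome, one test and one threshold, and the test is valid; ANCOVA is merely another valid estimator that is usually tighter. That is right, and it fixes the weight of the point: a recommended improvement, not a flaw that invalidates the trial.

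Second, the 28–30% figure rests on ρ = 0.4, an input that does not reproduce the plan's own power statement. If 57 m, 80% and SD 104 m are kept instead, ρ must be about 0.76–0.77 and the gain is about 10%, with power moving from 78% to 82% at 0.76. This stands as a limit on size. Even so, 0.4 is the only correlation the plan states.

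Third, equal SDs may not hold. The Statement of the Problem says that "the increase in exercise capacity among completers is variable", which may point to a larger spread at follow-up. This also stands: at 1.2 times the baseline SD the gain is roughly halved at ρ = 0.4 and gone at 0.76. Neither point reverses the recommendation, because the possible loss is about 2% and the possible gain is about 30%.

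Finally, one might fear that ANCOVA changes the question or disrupts the other planned analyses. With baseline in the model, change and follow-up distance as outcome give the same treatment estimate, and both the no-change imputation and the rank-based fallback carry over.

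**Conclusion.** The concern holds. The primary test is unadjusted, and the efficiency-motivated ANCOVA omits baseline walk distance although the value is in hand. Under the plan's stated inputs and equal SDs, the omission forgoes a 28–30% variance reduction, roughly the information from 10 more patients per arm. Over the other inputs examined, the gain runs from that figure down to nothing, with a loss of at most about 2%. The planned analysis remains unbiased with correct type I error. Adjustment does not rescue the stated 80% power at 57 m, which fails for separate reasons: at ρ = 0.4 the ANCOVA would itself need 46 per arm. The change should be made, as an improvement in precision.

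**What to change.** Before outcome data are seen, amend the Statistical analysis section as follows.

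- Make the primary analysis an ANCOVA of end-of-treatment 6-minute walk distance on treatment group and baseline 6-minute walk distance, two-sided 0.05.
- Add baseline walk distance to the wider covariate-adjusted model.
- Keep the unadjusted change-score ANOVA as a sensitivity analysis.
- State how the existing provisions carry over: no-change imputation sets the follow-up distance equal to baseline, and the rank-based fallback also adjusts for baseline.
- Because secondary outcomes are to be analysed similarly, adjust each for its own baseline where one exists, as for the WHODAS II.

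The cost is SAP wording and one residual degree of freedom. No new data are needed and no patients are lost, since the change score already requires the baseline value.

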There are a number of potential benefits to participants. All participants who undergo sleep apnea screening will be provided information on the results of their sleep studies, which may be useful in further health management. Participants randomized to CPAP may experience direct benefit related to treatment of underlying obstructive sleep apnea. There are also potentially important benefits to others, if the study confirms improved response to cardiac rehabilitation in those treated with CPAP.

Importance of the knowledge to be gained

The societal benefits to the study include an understanding of the extent to which treatment of obstructive sleep apnea, a highly prevalent comorbid condition in patients with coronary heart disease, will improve response to cardiac rehabilitation. If an improvement is demonstrated, this should lead to a change in practice patterns for the millions of adults who are enrolled in cardiac rehabilitation programs, with routine screening for and treatment of sleep apnea at the initiation of cardiac rehabilitation.

Data Safety and Monitoring

As described above, frequent contact will be maintained with participants throughout their participation in this study, with contact at 2, 4 and 6 weeks after randomization to ascertain sleepiness, hospitalizations, illnesses or other adverse events. The PI and staff will meet on a weekly basis to review study progress and adverse events. The PI will, on a weekly basis, review all data collected to assure that no physiological findings warrant immediate intervention. If so, the participant will be contacted and advised of the findings and offered assistance with appropriate referrals. Data from the Cardiopulmonary Exercise Testing procedures will be reviewed by a cardiologist-investigator and any unusual or adverse findings will be communicated to the participant's primary care physician or Cardiologist. Adverse events (classified by severity and unexpected/expected) will be defined and reported to the IRB in accordance with the rules regulating each severity class (expected vs unexpected, serious vs. other, related vs. unrelated). No Data and Safety Monitoring Board is envisioned.

Resources

Research Space

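### The primary test may change form once the data are seen, with no operational rule, and the change would move the result off the mean difference in metres on which the trial is planned

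*Combined protocol and SAP*

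**What the plan says.** The Statistical analysis section defines the primary test as a "one-factor analysis of variance comparing the mean changes from baseline in six minute walk distance", and then adds: "The primary analysis is a simple analysis of variance, with data transformation or adoption of rank-based inference if approximate normality is not present". The decision threshold is "A p value <0.05 will be considered statistically significant"; sidedness is not given. Secondary outcomes are to be handled in the same way, so they inherit the same open choice.

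The section also plans covariance models adjusting for age, sex, apnea severity, comorbidity, smoking and alcohol. Baseline walk distance is not on that list, although the baseline visit section takes the six minute walk result from the rehabilitation intake note.

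Sample size and power works in metres throughout: "the sample size of 25 subjects in each group will have 80% power to detect a difference between groups of 57 m". It sets the published effect of 114 m against a clinical threshold on the same scale: "This is well above the minimal clinically important difference of 23 m in 6-minute walk distance".

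The Randomization section lists the roles blind to assignment. A statistician or analyst is not among them.

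**The concern.** ANOVA is the named default and a condition for leaving it is given, but the condition cannot be applied as written. The plan does not settle:

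- whether normality is judged by a test, a plot or a threshold;
- whether it is judged on raw changes or residuals, and pooled or by arm;
- who judges it, and whether before or after unblinding;
- whether a transformation or a rank method comes first, and which one of each;
- how the treatment effect would then be reported.

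Two things are at stake. Two competent analysts could follow this text, run different confirmatory tests on the same data and reach different verdicts. And the alternatives do not test the same quantity as the default, so a switch could leave the confirmatory result on a scale that does not map directly to 57 m or 23 m.

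**Working it through.** **1. The plan's own figure.** Inputs from Sample size and power: SD 104 m, 25 per arm, difference 57 m, and "Assuming a modest correlation of 0.4 between repeated measures of the 6-minute walk test". Two-sided 0.05 is assumed.

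- SD of change = 104 × √(2 × (1 − 0.4)) = 113.9 m.
- Standard error of the difference = 113.9 × √(2/25) = 32.2 m, and 57/32.2 = 1.77.
- Power ≈ Φ(1.77 − 1.96) = 42%, or 41% by noncentral t.

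The stated 80% is not reproduced. It would need an SD of change of 57 / (√(2/25) × (1.96 + 0.84)) ≈ 72 m, or a correlation of 1 − 72²/(2 × 104²) ≈ 0.76. That is a separate issue; the 41% serves here only as a reference.

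**2. What each permitted analysis tests.**

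| Analysis | Quantity | Comparable with 57 m and 23 m? |
|---|---|---|
| ANOVA of change | Mean difference, metres | Yes |
| ANOVA after transformation | Difference of means on another scale | Not directly |
| Rank test | Stochastic ordering | Only through a Hodges-Lehmann shift, under a shift model |

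Changes can be negative, so a log or square root needs an offset that the plan does not state. If the mean gain were 50 m (an assumption, not in the documents), Φ(−50/114) = 33% of changes would be negative, or Φ(−50/72) = 24% at the SD implied by the stated power.

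**3. Type I error.** Simulated: 20,000 trials per shape, 25 per arm, SD 113.9 m. The shapes are assumed. The written rule is Shapiro-Wilk on residuals at 0.05, then t or rank.

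| Shape | t (ANOVA) | Rank | Written rule | Smaller p of t, rank | Smallest p, shifted log added |
|---|---|---|---|---|---|
| Normal | 5.1% | 4.7% | 5.2% | 5.8% | 6.8% |
| t, 3 df | 4.5% | 5.0% | 5.4% | 6.4% | 6.9% |
| Lognormal | 4.3% | 4.9% | 4.9% | 6.5% | 6.9% |
| Contaminated normal | 4.7% | 4.7% | 5.0% | 6.1% | 6.6% |

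**4. Agreement and power at a true 57 m.**

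| Shape | t power | Rank power | Verdicts differ |
|---|---|---|---|
| Normal | 41% | 39% | 7% |
| Gamma, shape 2 | 43% | 53% | 15% |
| t, 3 df | 50% | 64% | 18% |
| Contaminated normal | 44% | 51% | 14% |
| Lognormal | 49% | 81% | 32% |

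Under skew or heavy tails the disagreement is mostly the rank test finding a real effect that the t test misses: 12.9% of trials against 2.0% the other way for the gamma shape.

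**5. Adding baseline walk distance.** With the same inputs:

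- Residual SD = 104 × √(1 − 0.4²) = 95.3 m; standard error = 95.3 × √(2/25) = 27.0 m; 57/27.0 = 2.11.
- Power ≈ Φ(2.11 − 1.96) = 56%, or 54.5% by noncentral t, against 41.1% for ANOVA of change. The gain is 13.4 points.

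The gain depends on the correlation, because the variance ratio is (1 + r)/2: 0.70 at r = 0.4 and 0.88 at r = 0.76. At 0.76 the residual SD is 104 × √(1 − 0.76²) ≈ 68 m, and power moves from 80% to about Φ(57/(68 × √(2/25)) − 1.96) ≈ 84%.

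**The case against.** The strongest reply is that ANOVA is named as primary, that the trigger is the shape of the data and not the p value, and that the switch has a real benefit. All of that stands. A conditional rule, once written down, keeps the error near 5%, and a rank test can be much more powerful when changes are skewed or heavy-tailed. In the shapes above, a fixed unadjusted t test gives up about 10 to 14 points for the gamma and t (3 df) shapes, and between 7 and 32 across all the non-normal ones. A complete rule applied to pooled blinded data would therefore also be a defensible repair. What it would not repair is the change in the quantity tested.

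It can also be said that a rank analysis may report a shift in metres, and that the covariance models give supportive estimates in metres in any case. Both are true, so a switch would not leave the trial without any estimate in metres. But the shift equals the mean difference only under a shift model, and the covariance models are not the confirmatory test.

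A reader might infer from the Data Safety and Monitoring section ("The PI will, on a weekly basis, review all data collected") that the choice of test would be made unblinded. The documents do not support this. That review looks for findings needing immediate action, nothing says it is by arm or that the PI selects the test, and the Randomization section keeps the physicians who oversee the study blind. The supportable point is narrower: the analyst's blinding is unstated, and nothing fixes the choice before unblinding.

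**Conclusion.** The point holds as a specification gap in the only confirmatory test. The plan lets the observed distribution replace the primary analysis with an unnamed method, without an operational trigger or a timing requirement, and the replacement would not test the mean difference in metres used for planning.

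It should be corrected, but it is not fatal. A reader might take 6–7% as the plan's false-positive rate; that figure describes picking the smallest p value, which the text does not license. Nor is there no criterion at all: a qualitative one is given, but not one that can be applied. Non-normality alone is no reason to abandon ANOVA on grounds of error control, since the fixed t test stayed at 4.3–5.1% in every shape in the error table.

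The simulated figures rest on assumed outcome shapes and an SD of 113.9 m. The gain from about 41% to about 55% rests on the plan's SD and correlation, a two-sided test and approximate normality, and is smaller if the true correlation is higher.

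**What to change.** Replace the sentence on transformation and ranks with one primary analysis that holds whatever the distribution: the between-group mean difference in six minute walk distance, in untransformed metres, from a linear model with treatment and baseline walk distance, reported with its 95% CI. If distribution-free validity is wanted, take the p value from a permutation test of that same difference. Name one rank analysis (for example Wilcoxon-Mann-Whitney with a Hodges-Lehmann estimate) as a sensitivity analysis that cannot replace the primary result. State that secondary outcomes follow the same rule, and reconcile the existing covariate list with the new primary model.

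This costs a few sentences. The baseline measurement is already collected, and patients, visits and sample size are unchanged. The statistical price is power relative to a rank test under marked skew or heavy tails. The 13-point gain from baseline adjustment roughly covers the 7 to 14 points lost in the milder shapes, but only part of the 32 points in the lognormal case.

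### Adherence to cardiac rehabilitation, a secondary outcome, falls under follow-up-completer and no-change rules that do not fit it

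*Combined protocol and SAP*

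**What the plan says.** Study Design lists the secondary outcomes: "Secondary outcome measures include measures of functional status and health related quality of life, and adherence to cardiac rehabilitation". Statistical analysis gives them one rule: "Each of the secondary outcome measures is continuous; therefore, analysis of these variables will be treated in a similar fashion" to the primary. The primary analysis is a one-factor ANOVA of mean change from baseline in six-minute walk distance, with a transformation or rank-based method if normality fails.

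Two further rules in that section are worded generally:

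- Analysis set: "The main analysis will include all subjects completing the follow-up examination".
- Sensitivity analysis: a no-change result "will be imputed for all dropouts, and compared to the main analysis".

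The plan's reason for relying on these is that "the rate of dropouts during the course of the three-month trial is expected to be low" and that "we do not expect dropouts to be differential with respect to treatment group assignment". It gives no dropout rate.

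On data sources, Cardiac Rehab Assessment Measures says that information from the initial rehabilitation assessment "will be pulled from the Cardiac Rehabilitation exercise evaluation note in CPRS", and that "responses to World Health Organization Disability Assessment Scale II" are also recorded. Final study visit adds the walk test and WHODAS II taken at the end of rehabilitation. Neither section names an attendance or adherence measure.

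**The concern.** A walk test has a value before treatment and a value after it. Adherence to a programme has only the second. A rule built on change from baseline, with no change as the fallback for dropouts, therefore has nothing to act on when the outcome is adherence.

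The analysis set raises a second question. The Background section says that many patients who enrol in rehabilitation do not finish it, so stopping early is part of what this outcome should capture. If people who stop attending are also less likely to return for the study's final visit, the completer rule drops the participants who carry the information. The adherence comparison could then be shrunk, enlarged or created by who came back, and the plan would have no usable check.

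**Working it through.** **What the rules mean for each outcome**

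| | Six-minute walk, WHODAS II | Adherence to rehabilitation |
|---|---|---|
| Baseline value | Taken from the initial rehabilitation assessment | None listed, and none could exist |
| Change from baseline | Defined | Undefined |
| No change for a dropout | Zero | Undefined |
| Value if the final visit is missed | Not obtained if there is no end-of-programme assessment | May still be known, if attendance is recorded |

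The first three rows need no assumption about dropout. If the similar-fashion wording means an ANOVA of the post-baseline value, the change-score problem goes away. The completer restriction stays, and the sensitivity analysis still has no value to impute.

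**Size of the selection effect**

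The documents give no adherence figure and no dropout rate, so there is no figure of the plan's own to reproduce. The only input taken from them is 25 randomised per arm. The rest is assumed: the true programme completion rate *p* is 60% in both arms (no treatment effect), and everyone lost to follow-up is a quitter. This is the most selective kind of loss.

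If a fraction *m* of an arm is lost, the completion rate among those followed up is *p*/(1 − *m*).

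- CPAP, 1 of 25 lost: 0.60/0.96 = 15/24 = 0.6250
- HLSE, 3 of 25 lost: 0.60/0.88 = 15/22 = 0.6818
- Spurious difference: 0.6250 − 0.6818 = −0.0568, or 5.7 points against CPAP. Reversing the losses gives 5.7 points in its favour.
- Standard error: √(0.6250 × 0.3750/24 + 0.6818 × 0.3182/22) = √(0.00977 + 0.00986) = 0.140
- Ratio: 0.0568/0.140 = 0.41

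With equal loss of 2 of 25 per arm, both arms show 0.60/0.92 = 0.652 and the spurious difference is zero. Equal loss would stretch a real difference by 1/(1 − 0.08) = 1.087, or about 9%.

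The illustration uses binary completion. It carries over in proportion to mean sessions attended only if completers and quitters each have a fixed mean attendance, the same in both arms and the same for lost and retained quitters.

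**Separate point: precision for WHODAS II**

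The adjustment covariates in Statistical analysis are age, sex, apnea severity, comorbidity, smoking and alcohol. Baseline values of the outcomes are not among them. With equal variances σ² and baseline-to-follow-up correlation *r*:

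- Change-score variance: 2σ²(1 − *r*)
- ANCOVA residual variance: σ²(1 − *r*²)
- Ratio: (1 + *r*)/2

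At *r* = 0.4 the ratio is 0.84/1.20 = 0.70. At *r* = 0.8 it is 0.36/0.40 = 0.90. The plan assumes 0.4 for the walk test. It gives no value for WHODAS II, so this range is assumed.

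**The case against.** The strongest reply is that the rules reach adherence only by inference. The text says similar, not identical, and neither the completer rule nor the imputation rule names adherence. A sensible analyst would run the ANOVA on post-baseline attendance. That is a fair reading, and it disposes of the change score. It does not dispose of the analysis set or of the empty sensitivity analysis.

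A second reply is that the completer rule concerns the study's follow-up examination, not the rehabilitation programme. Someone who leaves rehabilitation may still attend the 8-week visit. This stands: a link between the two is plausible, since the follow-up walk test and WHODAS II come from the end of rehabilitation, but the documents do not show it.

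A third is that the illustration assumes the worst kind of loss and a threefold imbalance that the plan does not expect, and that even then the distortion is well under one standard error. This also stands.

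Three stronger readings might be inferred, and the documents support none of them.

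- *The adherence comparison will be biased.* That needs loss that depends on adherence and differs by arm, and nothing in the text establishes either.
- *Sessions attended before randomisation bias the result.* Recruitment allows screening on the day of rehabilitation intake, so some sessions could come first. The documents do not say when sessions begin, and any such sessions would be balanced between arms in expectation. They add noise, not bias.
- *The primary analysis is undermined.* Six-minute walk distance has a baseline, so this point about adherence does not touch it.

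**Conclusion.** The concern holds in a limited form. The plan applies to adherence a sensitivity rule that cannot be carried out, and an analysis set that may exclude poor adherers. The first part follows from the text alone. The second is a risk whose size cannot be derived from the documents. It is small if dropout is as low and non-differential as the plan expects, and the assumed case above puts it at 5.7 points, about 0.4 of a standard error. The plan has no working check for adherence if that expectation fails.

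The change is worth making because the alternative is less open to bias and cheap. It affects one secondary outcome. The WHODAS II suggestion is a precision gain and does not correct an error.

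**What to change.** Exempt adherence from the change-from-baseline, completer and no-change rules. In their place:

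- Define adherence as post-randomisation attendance, for example the proportion of scheduled sessions attended in a fixed window. Set the window once the passages giving 8 weeks and those giving three months of treatment have been reconciled.
- Compare it in all randomised participants by assigned arm, whether or not they attend the final visit, using the plan's existing rank-based option if needed.
- State how early stoppers and missing attendance records are counted.

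The cost is analysis-plan wording and possibly one data field. The study already takes the initial rehabilitation assessment from CPRS, but the documents do not say that attendance is recorded there. Its availability for every randomised participant must be confirmed first.

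Separately, analyse WHODAS II by ANCOVA on its baseline value, which is already recorded and needs no new data.
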